The Oculus/Meta Quest VR devices are non-invasive, relaxation devices that are commercially and widely available to deliver mobile (untethered) VR content to the patient; they are not FDA regulated. Both devices are all-in-one headsets, so no additional hardware is required to deliver the VR experience. These devices have audio capabilities built into the headset to deliver instructions and application sounds, creating an immersive experience. We have used these devices in multiple IRBs since 2018 without any adverse events. Each VR headset will be cleaned with an alcohol or peroxide wipe according to infection control standards following use of the device by the patient as well as prior to use for each patient and may undergo further cleaning with UV light using the Cleanbox (<https://cleanboxtech.com/>).

VR session. All participants will receive a device tutorial at the start of the study which will entail teaching them how to use the device and introducing them to the VR-BF software. They will be taught how to sync their breathing with the application. Patients will be instructed to remove the device should any discomfort or side effects occur, such as motion sickness, dizziness, or nausea.

FOREVR VR. FOREVR VR is the result of the collaboration between our research team, engineers at the Digital Experience (DX) Center at Cincinnati Children's Hospital, and programmers at House of Moves, an animation and motion capture studio in Los Angeles, California. FOREVR VR integrates real-time patient physiological data into a gamified environment using a chest strap (to monitor respiration) and an ear clip (adapted from HeartMath, see below) to measure heart rate. This technique is effective in reducing respiratory rate, and consequently, increasing heartrate variability.^{20,97} This increased heartrate variability increases vagal tone, resulting in activation of the parasympathetic response and decreased pain.⁹⁷

VR-BF content. We currently have two game options for use with the FOREVR VR device. The first is a 360-video shot in Eden Park (a public park in Cincinnati, OH) that starts out as a stand-still, black and white image that adds color and eventually motion as the participant achieves target heart rate and respiratory rate targets. The second is a blooming flower scene that starts with a clean, blank scene that allows the participant to have a flower appear and fully bloom as he/she achieves target physiological parameters.

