We are currently finalizing the *Mysterious Island* game with House of Moves which we plan on using for the study once it becomes available. In this game, participants will be transported to a beautiful tropical island in which the participant will use breath to explore the island. As the patient breathes in, they will make a small rise in the VR world upwards and breathing out will propel forward movement. The motions are small and gentle to minimize the risk of motion sickness. The entire VR space syncs with the patient's breathing. During the course of the experience, the participant will travel through a sunny island full of palm trees, caves, and tropical flowers. The user will move towards a beach to watch the sunset. The user will also encounter several tropical animals and birds. The VR world will combine a total of 3 locations: a tropical island and trail going to the entrance of a cave, the cave, and a beach. On the tropical path, the user will encounter a waterfall, up to 5 different tropical birds, and 2 different animals (hippo and monkey). This experience in its entirety will take up to 10 minutes.

Back-Up Technology. This is the first study to use FOREVR VR. Although we anticipate success with its use, we appreciate the difficulties of using any new technology. We therefore have a

Feasibility and Acceptability of Technology-Based Interventions in the Perioperative Setting

back-up plan in place using existing technology. Should it be necessary, we will use the Oculus/Meta Quest with the *Mindful Aurora* application and monitor heart rate/heart rate variability with the commercially available HeartMath Inner Balance device (www.heartmath.com). HeartMath is a program that is used clinically at Cincinnati Children's Hospital to teach biofeedback and that can document a patient's use of the application and heart rate/heart rate variability. The Inner Balance device integrates directly with a participant's smart phone device. HeartMath products are currently used in over 500 institutions. From a research perspective, they have been used in over 11,500 subjects resulting in over 400 peer-reviewed publications. Analogous to FOREVR VR, it uses an ear clip to measure heart rate. It stores information about use and performance in an application that is accessible to the research team. [name], one of the co-investigators, is an expert in the use of HeartMath for biofeedback.

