Dosing. To finalize VR-BF dosing prior to the efficacy trial, data will be collected on the number of daily practice (preoperative) and therapy (postoperative) sessions completed by each patient, duration of each session, changes in HRV and respiratory rate, and achievement of target HRV and respiratory rate parameters. We will also assess the total daily dose of sessions by totaling the duration of all sessions per day and assessing the mean and variability of the total daily dose. Achievement of target physiological parameters will be assessed by calculating the percentage of time a patient spends within specified targets for each session. Consistency in achieving target HRV and respiratory rate parameters will be defined as a binary outcome (yes/no) when the target range is achieved $\geq 75\%$ of the time during use (by session and by day). We will run descriptive statistics on duration of each session stratified by sessions achieving consistency (or not) and on frequency and duration of daily use by days achieving consistency (or not). Mean duration per session and mean duration and frequency per day in the group achieving consistency will be used to guide minimal dosing in the efficacy trial. **Exploratory analysis.** We will examine the association of VR-BF dose (frequency and duration of use) with the change in target physiological parameters to help identify the minimal dose (frequency and duration of use) required to reach consistency in achieving these targets. We will also examine the correlation between pain score reduction and VR-BF use (frequency and duration). We will calculate mean changes in pain score before and after VR-BF and mean frequency and duration of VR-BF use for each patient. We will visualize any correlation using a scatter or box plot and quantify the correlation using Spearman or Pearson correlation coefficients between two continuous variables

Feasibility and Acceptability of Technology-Based Interventions in the Perioperative Setting

and two sample t-tests or Wilcoxon rank-sum tests, as appropriate, between a continuous and categorical variable. Regression on changes in pain score will be used to examine linear or nonlinear correlations between pain reduction and VR-BF use. The same analysis will be repeated for opioid use (mg/kg/day) and patient-reported anxiety scores.

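### If VR-BF sessions include a start-up period, the 75%-of-use-time rule for consistency can favour longer sessions without better control, and the plan has no measure that would show it (cheap improvement)

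*Combined protocol and SAP*

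**What the plan says.** All of the rules are in section 17.0, Aim 2.

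- The basic measure is a share of session time: "Achievement of target physiological parameters will be assessed by calculating the percentage of time a patient spends within specified targets for each session".
- It is then cut to yes/no: "Consistency in achieving target HRV and respiratory rate parameters will be defined as a binary outcome (yes/no) when the target range is achieved" for at least 75% of use time, once per session and once per day.
- Durations and frequencies are described by that yes/no result, and the result feeds the next trial: "Mean duration per session and mean duration and frequency per day in the group achieving consistency will be used to guide minimal dosing" there.
- The exploratory analysis relates frequency and duration of use to change in the physiological parameters, "to help identify the minimal dose (frequency and duration of use) required to reach consistency in achieving these targets".

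On how a session begins, section 6.0 (VR-BF content) says that one scene opens still and in black and white, and "adds color and eventually motion as the participant achieves target heart rate and respiratory rate targets". The other opens blank, and a flower appears and blooms as targets are met. The documents give no time to target, no exclusion of start-up time and no minimum session length for scoring.

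**The concern.** Session length is the quantity to be learned, and it is also the denominator of the measure used to sort sessions into consistent and not consistent. If the opening minutes are spent getting into range, they take up a larger share of a short session than of a long one. Two sessions with the same time to target and the same control afterwards can then fall on opposite sides of the 75% cut only because one lasted longer.

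At stake is the dosing guidance carried into the efficacy trial. Table 2 names finalization of the VR-BF dose as a goal of Aim 2, and section 17.0 lists a dosing strategy among the anticipated outcomes.

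**Working it through.** **The plan's own figure.** The only calculated design figure is the Aim 2 sample size, and it reproduces. At 80% the exact 95% interval with n = 56 has width 0.223, and 56/0.80 = 70. The present point does not depend on it. The 75% cut is a definition, with no derivation to check.

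**Inputs.** From the documents: the 75% cut on use time, and the 10-minute reference session (Aim 1 research design, section 6.0). Assumed, because the documents give no values: start-up period r, share in target after start-up q, and the spread of session lengths.

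**Session level.** Share = q(d − r)/d.

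- If target is held after start-up (q = 1), 1 − r/d ≥ 0.75 gives d ≥ 4r. For r = 1, 2, 2.5, 3 and 5 minutes, the shortest qualifying session is 4, 8, 10, 12 and 20 minutes.
- If q < 1, the average share reaches 75% when d ≥ rq/(q − 0.75). With r = 2 and q = 0.9 this is 1.8/0.15 = 12 minutes.

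**Effect on the mean that guides dosing.** Simulation of 200,000 sessions: d about 10 minutes (SD 3), r lognormal (log-SD 0.5) and independent of d, target held once reached.

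| Median lag (min) | Mean duration, consistent sessions (min) | All sessions (min) |
|---|---|---|
| 0.5 | 10.1 | 10.0 |
| 1 | 10.3 | 10.0 |
| 2 | 11.0 | 10.0 |
| 2.5 | 11.3 | 10.0 |

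At the 2.5-minute lag, about 19% of sessions under 8 minutes, 49% of those of 8 to 12 minutes and 73% of longer ones count as consistent. Mean duration is 11.3 minutes in consistent sessions and 8.8 in the others.

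**Imperfect control.** With q = 0.9 (in/out-of-target process, autocorrelation time 1 minute), the three bands give 56%, 71% and 78% at a 1-minute median lag, and 21%, 43% and 57% at 2 minutes.

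**No lag.** The mean share is then flat in d. With q = 0.70 it is 0.70 at 5, 10, 20 and 30 minutes. The chance of passing the cut still depends on length:

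| q | 5 min | 10 min | 20 min | 30 min |
|---|---|---|---|---|
| 0.60 | 0.36 | 0.26 | 0.17 | 0.12 |
| 0.70 | 0.50 | 0.46 | 0.40 | 0.36 |
| 0.90 | 0.85 | 0.88 | 0.92 | 0.96 |

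The direction therefore reverses with q. With lengths of 5 to 30 minutes in equal proportions (mean 17.5), mean duration in consistent versus other sessions is 14.0 versus 18.4 minutes at q = 0.60, and 17.8 versus 14.2 at q = 0.90.

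**Day level.** With k sessions totalling T minutes and target held after each start-up, share = 1 − kr/T.

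- T fixed at 40, r = 2: k = 1, 2, 4, 8 gives 0.95, 0.90, 0.80, 0.60.
- Sessions of 10 minutes each (T = 10k), r = 2: 1 − 2/10 = 0.80 for every k.

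**The case against.** A reader might infer that consistency rises with session length by arithmetic alone. It does not. A share of time is already divided by length, and the rise needs a lag that the documents never quantify. Without a lag the sign can go either way. If control fades (say 90% in target for 10 minutes, then 50%), the share falls from 0.90 at 10 minutes to (9 + 5)/20 = 0.70 at 20 minutes.

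A reader might also infer that the rule pulls the dose toward long, infrequent sessions. That holds only if total daily minutes are fixed. The Aim 1 design sets a daily minimum and allows free extra use, so extra sessions may simply add minutes. If they are of equal length, the day share does not change.

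The lag may also be small. Patients are trained and practise for a week before surgery, and the scene descriptions support a start-up period in kind only. At a 1-minute median lag the mean that guides dosing moves by 0.3 minutes. For the island scene, "This experience in its entirety will take up to 10 minutes", which may limit how far session lengths vary.

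Finally, the yes/no measure does not stand alone. The plan also computes the continuous percentage of time in target, examines change in the parameters and the correlation of use with pain scores, and collects interview data. The means only guide dosing, and no benchmark in Table 3 uses consistency.

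All of this stands as a limit on size and direction. It does not remove the point: none of these analyses separates time to target from control after target, so the plan could not tell a length artefact from a real dose effect.

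**Conclusion.** The point holds conditionally. If sessions begin with a start-up period and target is then well held, the 75% rule favours longer sessions without better control, with the threshold at 4r when target is fully held. Under the assumptions above, the mean that guides dosing shifts by 0.1 to 1.3 minutes on a 10-minute session for median lags of 0.5 to 2.5 minutes. With no or short lag and control at or below about 70%, the relation is flat or reversed. The documents do not establish the direction, and the frequency effect is confined to fixed daily minutes.

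The consequence is for planning the efficacy trial. This trial's feasibility and acceptability results are not affected. It is a cheap improvement, not a flaw in the trial.

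**What to change.** In section 17.0 (Aim 2, Dosing), keep the 75% measure as a description and derive two more quantities per session from the device time series:

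1. time to first reaching target;
2. the continuous share of time in target after that point.

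Relate duration and frequency to these two instead of relying on the yes/no result alone. Label sessions that never reach target as such.

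Two tempting alternatives are worse. Minutes in target is d − r, so it follows duration even more closely than the share does (correlation 0.90 against 0.54 in the simulation with a 2.5-minute median lag). An early fixed window used alone cannot show fading or what length is needed.

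The cost is SAP wording and a little more analysis of data that section 6.0 already collects. One downside is that the second measure is undefined for sessions that never reach target. It also begins in target by construction, which slightly favours a short remainder. With q = 0.9 and a 1-minute autocorrelation time, the excess over a remainder of L minutes is about (1 − q)/L, or 0.1/8 = 0.0125 for 8 minutes.

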sampling will be used to select a representative patient group according to age, sex, and race. We anticipate recruiting about 1 patient per week. Patients will be identified when scheduled for surgery. They will receive scripted instruction on the Oculus/Meta Quest and a tutorial on the biofeedback application. Once device and content education are complete, patients will receive manual-based training on the benefits of HRV BF.⁵⁶ They will be given the appropriate equipment and instructed to complete an independent daily, 10-minute session (based on the standard duration of a BF session) and record each session in a log. Patients will bring the equipment to the hospital on the day of surgery for continuation into Aim 1b. After surgery, patients will have free use of VR-BF. They will be instructed to undergo, at minimum, one daily, 10-minute session. They will also be instructed to freely use VR-BF, particularly when in pain. They will use a log to record their VR-BF usage (date, time, and duration). Patients will be visited daily, or more or less frequently as applicable/needed, to assist with log completion and any issues. On the day of discharge, a study team member will conduct a detailed, semi-structured interview. Patients may take the VR-BF device home for up to two weeks for home pain management; a similar log will be used to document home use. We will enroll 4 patients at a time and analyze data to refine the protocol in an iterative fashion; this process will be repeated until 12 patients are enrolled. If further data is required for protocol refinement, we will continue recruiting patients in groups of 4 as necessary until a maximum number of 32 patients is reached.

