After surgery, as in Aim 1, a trained CRC will visit patients daily or as needed while hospitalized. Control group patients will complete a daily application-generated usage report (date, time, duration); VR-BF patients will have this information, along with HRV and respiratory rate data, obtained from the device. To help determine what outcomes may be impacted by VR-BF for future trial development, patients will also be asked to document pain and anxiety scores before and after each VR-BF or application session using the NRS.^{110,111} Patients will self-report and document these scores before each session and then immediately, 15 minutes, and 30 minutes after session completion. All pain scores and opioid consumption (in morphine equivalents mg/kg/day) will be collected from EPIC, the electronic medical record, for each 24-hour period during study enrollment; anxiety scores are not documented by the nursing staff so only self-reported scores will be used. Documented pain scores will also help finalize the “dose” of VR-BF to be used in the efficacy trial as we will assess for correlation, if any, between pain score and use of VR-BF. At the final study visit prior to discharge, patients will answer a questionnaire and engage in a semi-structured interview soliciting qualitative feedback about their experience with the intervention or control to finalize the study protocol for the clinical efficacy trial. Participants will be given the option to take the VR-BF platform home or continue using the *Manage My Pain* application for up to two weeks after discharge. If this option is selected, patients will complete a daily log/report documenting use, pain scores, and opioid consumption. During the first postoperative clinic visit, VR-BF and reports/logs will be collected and questions about home use will be asked, answered, and recorded. Parents will also be asked to complete a survey about their experience and opinions. If patients cannot be met during the first postoperative clinic visits, other arrangements will be made to collect the information and equipment.

Feasibility and Acceptability of Technology-Based Interventions in the Perioperative Setting

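### Minimal VR-BF dosing is to be guided by mean use among sessions and days that achieved consistency; that mean describes typical successful use and does not estimate a minimum

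*Combined protocol and SAP*

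**What the plan says.** The Dosing paragraph for Aim 2 (section 17.0) computes, for each session, the percentage of time within the HRV and respiratory rate targets. Consistency is then a yes/no outcome, reached when the target range is held at least 75% "of the time during use (by session and by day"). The plan adds: "We will run descriptive statistics on duration of each session stratified by sessions achieving consistency (or not"), with a parallel description of daily frequency and duration by day. The step from these data to a dose for the later efficacy trial is: "Mean duration per session and mean duration and frequency per day in the group achieving consistency will be used to guide minimal dosing".

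The exploratory paragraph that follows relates frequency and duration of use "with the change in target physiological parameters to help identify the minimal dose" needed to reach consistency.

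Other inputs to the dose are named in section 6.0 (Aim 2, Research Design). "Documented pain scores will also help finalize the" dose for the efficacy trial, and "At the final study visit prior to discharge, patients will answer a questionnaire and engage in a semi-structured interview soliciting qualitative feedback" to finalize the protocol.

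On usual use, the Aim 1 postoperative text says "They will be instructed to undergo, at minimum, one daily, 10-minute session" and "They will also be instructed to freely use VR-BF, particularly when in pain". The planned island game lasts up to 10 minutes and the back-up narrative lasts 10 minutes. For Aim 2, the preoperative instruction for control patients, given as parallel to the VR-BF group, is at least 10 minutes a day for seven days. Otherwise Aim 2 follows the protocol that Phase 1 will produce.

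**The concern.** A minimum is about where success starts to be lost as use falls. A mean taken only over successes carries no information on how often the same amount of use failed, or on whether less use would also have succeeded. When most sessions are long enough, the successes are nearly all of the sessions, and their mean is simply usual use. Instructions and content both pull usual session length towards 10 minutes, so this situation is plausible here.

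The frequency part has the same weakness. Consistency is a share of time during use, so a single-session day is consistent if its session is. If one session a day is usually enough, the mean number of sessions on consistent days still returns the usual number.

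Dose finalization is an Aim 2 goal (Table 2), and a dosing strategy is a listed deliverable (section 17.0, Anticipated outcomes). A figure labelled as a guide to minimal dosing would be carried into the efficacy trial without showing whether shorter or less frequent use also reaches target.

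**Working it through.** The documents state no figure for the minimal dose, so there is none to reproduce. The VR-BF arm that supplies the data has 35 patients, or 35 × 0.80 = 28 after the planned retention.

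**1. Session length.** Assumed inputs, none from the plan except the 10-minute anchor: length d ~ Normal(10, SD); probability of consistency 0.9 if d ≥ m and 0.1 if d < m, where m is the true minimum. With z = (m − 10)/SD, and φ and Φ the standard normal density and distribution function:

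- P(consistent) = 0.1 + 0.8 × [1 − Φ(z)]
- mean among consistent = 10 + 0.8 × SD × φ(z) / P
- mean among non-consistent = 10 − 0.8 × SD × φ(z) / (1 − P)

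Example, SD 3 and m = 4: z = −2, φ = 0.0540, 1 − Φ = 0.9772, so P = 0.8818. The consistent mean is 10 + 2.4 × 0.0540/0.8818 = 10.15. The non-consistent mean is 10 − 2.4 × 0.0540/0.1182 = 8.9.

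| SD | m (min) | P(consistent) | Mean, consistent | Mean, non-consistent |
|---|---|---|---|---|
| 3 | 4 | 0.88 | 10.15 | 8.9 |
| 3 | 6 | 0.83 | 10.5 | 7.7 |
| 3 | 8 | 0.70 | 11.1 | 7.5 |
| 1 | 4 | 0.90 | 10.0 | 10.0 |
| 1 | 6 | 0.90 | 10.0 | 10.0 |
| 1 | 8 | 0.88 | 10.05 | 9.6 |
| 1 | 12 | 0.12 | 10.4 | 10.0 |

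Doubling the minimum from 4 to 8 min moves the plan's guide by about 1 min at SD 3 and by 0.05 min at SD 1. With the minimum at 12 and SD 1, the guide falls below the minimum.

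**2. Link to the 75% rule.** Suppose a patient needs L minutes to settle and then stays in target. A session is consistent when (d − L)/d ≥ 0.75, that is, d ≥ 4L. Minima of 4, 6 and 8 min therefore correspond to settling times of 1, 1.5 and 2 min.

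**3. Frequency.** Assume 1 + Poisson(1) sessions a day (mean 2.0), lengths Normal(10, 3), the settling model, and time pooled over the day. Single-session days are consistent with probability 1 − Φ((4L − 10)/3) = 98%, 91% and 75% for L = 1, 1.5 and 2. By simulation, the mean frequency on consistent days is 2.0, 2.0 and 2.1. The mean daily duration is about 20 to 22 min, against a usual 20.0. In this model extra sessions do not raise the share of time in target, so the result illustrates the case where one session is usually enough; it is not evidence that this case holds.

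**4. Whether a model does better.** Assumed: 28 patients, 5 or 10 sessions each, patient random-intercept SD 1, logistic slope 0.5 or 1 per minute, 50% points at 4, 6 and 8 min, 1,000 runs per setting, logistic GEE. At SD 3 the median estimate is within about 0.2 min of each 50% point, and it lies inside the observed range of use in about 84–100% of runs. At SD 1 it lies inside that range in at most about 6% of runs (4 min), about 14–20% (6 min) and roughly 70–90% (8 min). The success-group mean in the same runs is 10.3–11.2 min at SD 3 and 10.0–10.2 min at SD 1.

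**The case against.** The strongest reply is that the plan already looks for a minimum. Its exploratory analysis is expressly aimed at the dose needed for consistency, and the stratified table includes sessions and days that failed. Both points are correct. A reader might infer that the plan ignores failures or has no minimum-seeking analysis; the documents do not support that. At SD 3 the non-consistent column is informative: the gaps between the two means are about 1.2, 2.8 and 3.6 min for minima of 4, 6 and 8. What remains is that the dosing sentence uses the success group only. The exploratory analysis takes change in physiological parameters as its outcome, and names no model, no required probability of consistency and no way of combining its result with the means.

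Second, the means only guide, beside pain scores and interviews, in a feasibility study without confirmatory testing. That limits the consequence. It also rules out the inference that the means alone will fix the efficacy-trial dose.

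Third, the remedy is weakest where the fault is worst: with session lengths clustered near 10 minutes, a model often cannot find a much lower minimum. This stands. The gain is then that the analysis says so, whereas the mean would report about 10 min.

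Fourth, one good session does not make any day consistent. If time is pooled, two equal-length sessions at 80% and 50% give 65%, and the day fails. Pooling is itself an interpretation of the by-day definition. The frequency argument is therefore confined to single-session days and to the case where one session is usually enough.

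**Conclusion.** The point holds and should be corrected. The success-group means do not estimate a minimum, and they are nearly insensitive to it when it lies well below usual use. That insensitivity is structural. The minutes are illustrations that rest on an assumed mean of 10, SDs of 3 and 1, and success probabilities of 0.9 and 0.1.

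A reader might infer that the rule always overstates the minimum. It does not: the guide rises when the minimum is near usual use, and it can fall below a minimum that exceeds most observed use. Nor do the documents show what the true minimum is, or that it is below 10 minutes. Aim 2 session length and its spread will be known only after Phase 1, apart from the preoperative instruction of at least 10 minutes a day. The weight is moderate: the analysis is exploratory, but it feeds a named Aim 2 deliverable.

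**What to change.** - Relabel the success-group means as typical use when consistent, and stop using them as the guide to minimal dosing.
- Keep the stratified descriptives. Add the observed proportion consistent by duration and by frequency, with the number of non-consistent sessions and days. State how multi-session days are pooled.
- Make the exploratory analysis the guide. Model the probability of consistency on session duration and, in separate day-level models, on daily frequency and on daily duration. Use all sessions and days, with patient-level clustering (for example logistic GEE), and report fitted curves with 95% CIs. Separate models are needed because daily duration and frequency are nearly collinear when session length is steady.
- State in advance the probability that counts as reaching consistency. The 50% point above is only for illustration.
- Label the result exploratory and observational, because use is partly self-chosen and may follow pain.
- Read no minimum outside the observed range of use. Report not located when few sessions fail or session lengths cluster.

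The cost is analysis wording and some programming; every variable is already collected or derived. With about 28–35 VR-BF patients the estimate will be imprecise, and if lengths cluster near 10 minutes the answer will often be not located. No dose is proposed.
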